## 2.2 Primary and secondary endpoints

The primary objective of this observational study is to objectify the subjective parameters indicated by the patient (pain, physical impairment, health-related quality of life, activity diary) and the objective parameters measured by the investigator (strength, trunk mobility and trunk fluctuations, sensory, neurodynamics, thickness of the subcutaneous fat layer, muscle fiber alignment and physiotherapeutic objectives).

The secondary objective includes the evaluation of possible relationships between the subjective and objective parameters.

Subjective parameters and their objectification:

- **health-related quality of life**

The health-related quality of life prevailing at the time of measurement is assessed using the German version of the SF-36. The patient fills out the questionnaire independently during the measurement appointment, without being influenced. The examiner adds up the total score achieved and transfers the value to the patient's data sheet.

Objectification of health-related quality of life:

SF-36 Questionnaire, German Version

- **Physical impairment**

The physical impairment prevalent at the time of measurement is assessed using the German version of the Oswestry Disability Questionnaire (ODQ). The patient fills out the questionnaire independently during the measurement appointment, without being influenced. The examiner adds up the total score achieved and transfers the value to the patient's data sheet.

Objectification of physical impairment:

Oswestry Disability Questionnaire, German version

- **Pain**

The pain radiation and the intensity of pain are subjectively assessed by the patient. For this purpose, he is given a sheet with a body chart (pain drawing). With 3 different colors (red = pain, yellow = paresthesia, green = numbness), the patient draws the current sensations at this measurement time. In addition, the patient is surveyed using the visual analogue scale (VAS 0 (no complaints) – 10 (maximum complaints)) to record the intensity of the complaints.

Objectification of radiation area:

The pain drawings are scanned and evaluated with the MATLAB software ([www.ch.mathworks.com](http://www.ch.mathworks.com)). Here, the radiation area is quantified as a percentage of the total body surface.

Objectification intensity:

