## 2.3 Project design

The study is a prospective observational study. There is no intervention. No influence is exerted on the normal physiotherapeutic and medical treatment of patients. At the Graubünden Cantonal Hospital in Chur, repeated measurements are being carried out. Therefore, a single-center study is available here.

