### 3.3 Study procedures

After oral study information by [name], after signing the written study information and declaration of consent and clarifying the inclusion and exclusion criteria (health questionnaire), the measurement points are planned. A total of 6 measurement points are determined. The first 5 appointments take place once a month, followed by a 3-month measurement-free period, after which the last and 6th measurement takes place. In the event of complications or worsening symptoms, the head of the study, who is also the attending physician, is informed immediately.

If a conservatively treated patient needs surgery during the study (e.g. due to a worsening of his symptoms), the preoperative data set will be recorded and a new postoperative data set will be opened, provided that the patient wishes to continue participating and/or is not excluded by the study management. The study includes conservatively treated (physiotherapy) and surgically treated patients equally.

If imaging techniques are used in the context of medical diagnosis, these images are included in the data collection and taken into account as far as possible in the interpretation of the data.

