**Planning of measurement dates**

During the first measurement, the test person is instructed and given to keep the activity diary with a protocol for taking painkillers.

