By the time a patient presents to the neurosurgery department, the back pain has already reached a high degree of severity. The duration and intensity of symptoms vary and should be stratified in evaluation. The measurement times should be strictly adhered to in order to ensure comparability in time between the test subjects.

The study ends in the 8th month after the start of the study after the 6th and last measurement.

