### **3.4 Withdrawal and discontinuation**

Participants will be excluded from the study if they do not (or cannot or do not want to) fulfill their obligations that entail participation in the study, or if they wish to voluntarily withdraw from participating in the study. Data that has already been collected is included in the data analysis as far as possible. If a conservatively treated patient needs surgery during the study (e.g. due to a worsening of his symptoms), the preoperative data set will be recorded and a new postoperative data set will be opened, provided that the patient wishes to continue participating and/or is not excluded by the study management.

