## **4 STATISTICS AND METHODOLOGY**

### **4.1. Statistical analysis plan**

The required number of subjects was determined a priori with G\*Power (version 3.1.9.2; Franz Faul University of Kiel, Germany). The following design specifications were used: statistical test = Correlation Type of Power Analysis 'Computer required sample size – given  $\alpha$ , power and effect size'; tails = two; effect size = 0.5;  $\alpha$  = 0.05; power = 0.95. The target number of subjects was  $n$  = 42 based on these design specifications. The SPSS version 24 software is used for statistical data analysis (IBM, Armonk, NY, USA).

The data are first checked for normal distribution with the 'Shapiro-Wilk test'. The normally distributed data are analysed by means of parametric test procedures. Non-normally distributed data as well as non-metric data are checked with non-parametric tests. The correlations are recorded using the 'Pearson Correlation tests' and 'Spearman Correlation tests'.

Correlations between the subjective parameters (pain, physical impairment, activity diary), between the objective parameters (strength, balance, sensory, neurodynamics, muscle thickness

and physiotherapeutic objectives), as well as between the subjective and objective parameters are of interest and should be calculated.

The following working (H1) and null hypotheses (H0) are statistically proven or rejected:

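### Six measurements per patient, but section 4.1 fixes neither the visit or patient-level summary that enters each correlation nor a method for repeated measures

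*Combined protocol and SAP*

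**What the plan says.** Section 2.3 describes the design: "repeated measurements are being carried out". Section 3.3 sets the number: "A total of 6 measurement points are determined". Five are monthly and the sixth follows a 3-month gap, 8 months in all. Sections 3.3 and 3.4 allow a second record for a patient who is operated on during the study: "the preoperative data set will be recorded and a new postoperative data set will be opened".

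The analysis is in section 4.1. After a Shapiro-Wilk check and a general split between parametric and non-parametric procedures, the only association methods named are these: "The correlations are recorded using the 'Pearson Correlation tests' and 'Spearman Correlation tests". The 17 hypothesis pairs that follow are plain statements of correlation between parameters, with no visit, mean, change score or time term. The sample size of 42 counts people: "The required number of subjects was determined a priori".

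Three other places bear on the choice of row:
- Section 3.3 on timing: "The measurement times should be strictly adhered to in order to ensure comparability in time between the test subjects".
- Section 4.2 keeps patients who miss visits, on the ground that individual relationships are being estimated.
- Section 3.3 on the diary: "During the first measurement, the test person is instructed and given to keep the activity diary with a protocol for taking painkillers".

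Section 1 adds a wish to follow the parameters over time and relate them to impairment and to the aims of physiotherapy. On rank, section 2.2 says: "The secondary objective includes the evaluation of possible relationships between the subjective and objective parameters". Section 2.1 lists the same kind of hypotheses under a heading that includes the primary objective. Either way, section 4.1 plans to test them.

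**The concern.** A Pearson or Spearman test takes its p-value from independent pairs, one per patient. The study will hold up to six pairs per patient for most variables, and possibly a further set after surgery. The plan does not say how these become one row.

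Three things follow. If the visit is chosen after the results are seen, or a hypothesis counts as shown when any visit is significant, the nominal 5% no longer holds. If visits are stacked as separate rows, it fails for a different reason, because rows from one patient are not independent. If a single visit is used, the error rate is sound, but most of the 8 months of data are not used for the aim in section 1. Section 8 expects several articles from these data, so the choice could also differ between papers.

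**Working it through.** **Inputs from the documents.** 42 patients; 6 measurements; correlation 0.5; two-sided α 0.05; power 0.95 (sections 3.3 and 4.1). **Assumed, because the documents give none:** the ICC, meaning the share of a variable's variance that lies between patients. It is set at 0.3 to 0.8, equal in both variables unless stated.

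**1. The plan's own figure.** With noncentrality √n × r/√(1 − r²) and n − 2 degrees of freedom, n = 42 gives √42 × 0.5/√0.75 = 3.74 and power 0.9545. It is the smallest n that reaches 0.95, so 42 is reproduced. The exact bivariate-normal model needs 46 and gives 0.935 at 42. Both models assume one independent pair per patient; neither says which pair.

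**2. False positives when there is no association** (simulated, 42 × 6, Pearson, 60,000 data sets per ICC).

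| ICC | Any of six visits significant | 252 rows pooled | Pooled, by formula |
|---|---|---|---|
| 0.3 | 26.0% | 10.1% | 10.4% |
| 0.5 | 24.9% | 19.1% | 19.1% |
| 0.7 | 21.3% | 29.3% | 29.1% |
| 0.8 | 18.2% | 34.3% | 33.9% |

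The formula is 2 × [1 − Φ(1.96/√D)] with D = 1 + 5 × ICC². At ICC 0.7, D = 1 + 5 × 0.49 = 3.45 and 1.96/√3.45 = 1.055, which gives 29.1%. Six fully independent tests would give 1 − 0.95⁶ = 26.5%, close to the any-visit rate at low ICC. Spearman results on log-normal data differ by at most about one percentage point. One prespecified visit, a patient mean or a change score each reject in about 5% (4.8–5.1%).

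**3. Do valid one-row choices agree?** Share of data sets in which the two choices fall on opposite sides of p = 0.05:

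| True r (between and within patients) | ICC | Measurement 1 vs 6 | Measurement 1 vs mean | Measurement 1 vs change score |
|---|---|---|---|---|
| 0.5 (planned) | 0.7 | 10% | 7% | 11% |
| 0.5 (planned) | 0.5 | 11% | 9% | 11% |
| 0.3 | 0.7 | 34% | 23% | 45% |
| 0.3 | 0.5 | 42% | 30% | 42% |

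At r = 0.3 a single test has only about 50% power. The same test in two independent samples would then disagree in 2 × 0.5 × 0.5 = 50%.

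**4. The row also sets the question.** The correlation at one visit is ICC × between-patient r + (1 − ICC) × within-patient r. At ICC 0.7:

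| Between r | Within r | Single-visit r | Single-visit power | Within-patient test |
|---|---|---|---|---|
| 0.5 | 0.5 | 0.50 | 93.5% | about 100% |
| 0.6 | 0 | 0.42 | 81.3% | about 5% |
| 0 | 0.6 | 0.18 | 20.7% | about 100% |

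**5. Check of a within-patient analysis.** A test centred by patient and visit, on complete data, rejects in 4.8–5.1% under no association. With residual correlation of 0.2, 0.3 or 0.5 per month (assumed, visits at 0, 1, 2, 3, 4 and 7 months) it rejects in 5.5%, 5.6% and 7.4%. The mixed model proposed below was not itself simulated.

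**The case against.** The best defence reads sections 3.3, 4.1 and 4.2 together. Timing is kept strict so that patients can be compared, patients with missed visits stay in because individual relationships are estimated, and 42 counts patients. The natural reading is then a correlation at each measurement point among those who attended, and each such test is valid. This stands in part: it gives pooling no support. But it leaves up to six results for each variable pair and does not say which one decides.

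A reader might infer four stronger things:
- **That visits will be pooled.** The plan does not say so. The 10–34% shows what an unexcluded choice would cost, not what will happen.
- **That section 4.1 names nothing but two tests.** It also mentions parametric and non-parametric procedures in general. None is specified as a repeated-measures method.
- **That conclusions would often flip.** The 23–45% disagreement arises at r = 0.3, mainly because power is low there. At the planned 0.5 it is 7–11%. The change-score comparison is also a stretch, since the hypotheses contain no change term.
- **That one fixed visit gives one 5% test per hypothesis.** It does not. Pain has an area and an intensity, and the first hypothesis pairs it with both impairment and quality of life. That is at least 4 tests, or 1 − 0.95⁴ = 18.5% for any false positive if they were independent (assumed).

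The over-time aim in section 1 is worded as a wish, and section 2.2 has no objective on change. That is a reason to analyse it as exploratory, not to leave it without an analysis.

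**Conclusion.** The concern holds as a gap in specification, and it should be fixed. The repeated visits and the possible second data set are in the plan. The row that enters each correlation is not, and neither is a method for within-patient dependence or an analysis of the aim in section 1.

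The cost depends on how the open choice is used. Per variable pair, the false-positive rate is about 5% with one row fixed beforehand, about 18–26% if any significant visit counts, and about 10–34% if visits are stacked. These ranges assume ICCs of 0.3 to 0.8, complete visits, and equal correlation between all visits of a patient. That the row is undefined follows from the text alone and needs none of these assumptions.

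**What to change.** In section 4.1:

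1. **Fix the row.** For each variable pair, state in advance one row per patient for the Pearson or Spearman test: one named visit (for example measurement 1, which later missed visits do not affect) or a patient mean. The diary is handed out only at measurement 1, so pair the diary hypotheses with a fixed later diary period and visit. State the time point for physiotherapeutic objectives, which have no row in the measurement overview. Say that the 5% level applies per variable pair, because several measures sit under each hypothesis.
2. **Handle the repeated visits.** State that visits are not treated as independent rows. For the aim in section 1, analyse all visits in SPSS with a method that allows for dependence. One example is a linear mixed model with a random patient intercept and visit as a factor, separating between-patient from within-patient association. Label it exploratory.
3. **Handle the second data set.** Keep one patient identifier across the pre- and postoperative data sets and count the patient once toward 42. State which data set supplies the row, including for a patient operated on before the diary visit.
4. **Keep the stratification** by duration and intensity of symptoms that section 3.3 asks for, and say how it enters these analyses.

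The cost is wording and slightly more analysis in software already named, with no new patients or measurements. The sponsor gives up the freedom to choose the visit later. A single visit can also miss a purely within-patient association, which would then appear only in the exploratory model.

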## 2 PROJECT OBJECTIVES AND DESIGN

### 2.1 Hypothesis and primary objective

The following working and null hypotheses are to be statistically proven or discarded.

Pain Drawing (VAS)

---

H0 There is no correlation between pain and physical impairment and health-related quality of life.

H1 There is a correlation between pain and physical impairment and health-related quality of life.

H0 There is no correlation between pain and activity diary.

H1 There is a correlation between pain and activity diary.

H0 There is no correlation between pain and strength and muscle fiber alignment.

H1 There is a correlation between pain and strength and muscle fiber alignment.

H0 There is no correlation between pain and trunk mobility and trunk fluctuations.

H1 There is a correlation between pain and trunk mobility and trunk fluctuations.

H0 There is no correlation between pain and sensory activity.

H1 There is a correlation between pain and sensory activity.

---

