#### Physical impairment, health-related quality of life (ODQ, SF-36)

H0 There is no correlation between physical impairment, health-related quality of life and activity diary.

H1 There is a correlation between physical impairment, health-related quality of life and activity diary.

H0 There is no correlation between physical impairment, health-related quality of life and strength.

H1 There is a correlation between physical impairment, health-related quality of life and strength.

H0 There is no correlation between physical impairment, health-related quality of life and trunk mobility and trunk fluctuations.

H1 There is a correlation between physical impairment, health-related quality of life and trunk mobility and trunk fluctuations.

H0 There is no correlation between physical impairment, health-related quality of life and sensory perception.

H1 There is a correlation between physical impairment, health-related quality of life and sensory perception.

H0 There is no correlation between physical impairment and thickness of the subcutaneous fat layer and muscle fiber alignment.

H1 There is a correlation between physical impairment and thickness of the subcutaneous fat layer and muscle fiber alignment.

---

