#### Strength (isometric force measurement of the affected characteristic muscles)

H0 There is no correlation between isometric force and trunk mobility and trunk fluctuations.

H1 There is a correlation between isometric force and trunk mobility and trunk fluctuations.

H0 There is no correlation between isometric force and sensing.

H1 There is a correlation between isometric force and sensing.

H0 There is no correlation between isometric force and thickness of the subcutaneous fat layer and muscle fiber alignment.

H1 There is a correlation between isometric force and thickness of the subcutaneous fat layer and muscle fiber alignment.

H0 There is no correlation between isometric strength and physiotherapeutic objective.

H1 There is a correlation between isometric strength and physiotherapeutic objectives.

H0 There is no correlation between isometric strength and physical impairment and health-related quality of life.

H1 There is a correlation between isometric strength and physical impairment and health-related quality of life.

---

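### Section 4.1 sets 17 hypothesis pairs to be proven or rejected, with no primary correlation, multiplicity rule or exploratory label, and sections 2.1 and 2.2 disagree on their status

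*Combined protocol and SAP*

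**What the plan says.** Section 4.1 sizes the study for one two-sided correlation test (effect size 0.5, alpha 0.05, power 0.95, n = 42). It then states "The following working (H1) and null hypotheses (H0) are statistically proven or rejected" and lists five hypotheses on pain, five on impairment and quality of life, four on force and three on trunk measures. Section 2.1 uses nearly the same formula: "The following working and null hypotheses are to be statistically proven or discarded".

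On status, the list in 2.1 stands under the heading Hypothesis and primary objective. Section 2.2 says "The primary objective of this observational study is to objectify the subjective parameters indicated by the patient", together with the investigator-measured parameters, and then "The secondary objective includes the evaluation of possible relationships between the subjective and objective parameters". The text of 4.1 asks for correlations within the subjective set and within the objective set, "as well as between the subjective and objective parameters are of interest and should be calculated".

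The two hypothesis lists are close but not identical. In 2.1 the last impairment hypothesis reads "H0 There is no correlation between physical impairment and thickness of the subcutaneous fat layer and muscle fiber alignment"; its counterpart in 4.1 adds health-related quality of life. The strength block of 2.1 also has "H0 There is no correlation between isometric strength and physical impairment and health-related quality of life", which 4.1 does not repeat there. The sentence in 4.1 on correlations "between the objective parameters (strength, balance, sensory, neurodynamics, muscle thickness" includes neurodynamics, which no hypothesis in either list mentions.

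**The concern.** The sentence introducing the list says what the tests decide: each hypothesis is settled one way or the other. With one nominal level, many tests and no ranking, that wording lets any result below 0.05 count as an established relationship. Section 1 says the inventory of relationships should support and improve physiotherapy, and section 8 foresees several articles. A reader of one article could not tell how many correlations had been examined, or whether the one reported was a planned main result.

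The joint hypotheses add a second gap. If pain correlates with strength but not with muscle fibre alignment, the plan does not say whether that H0 falls.

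**Working it through.** **The plan's own figure.** Inputs from 4.1: r = 0.5, two-sided alpha 0.05, power 0.95.
- Point-biserial model: noncentral t, df = n − 2, noncentrality r/√(1 − r²) × √n. At n = 42 this is 0.5/√0.75 × √42 = 3.74. Power is 0.955, and 42 is the smallest n reaching 0.95. The stated figure is reproduced, for one test.
- Bivariate-normal model (exact): 46 are needed, and power at 42 is 0.935. Fisher z agrees: ((1.960 + 1.645)/atanh 0.5)² + 3 = 46.1.

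**Counting hypotheses.** Section 4.1: 5 + 5 + 4 + 3 = 17. Section 2.1: 5 + 5 + 5 + 3 = 18. The eighteenth is strength against impairment and quality of life, which the impairment block of 2.1 already contains in reverse order.

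**Counting pairs in 4.1.** The wording does not fix this, so three readings are shown.

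| Block | All named constructs split | Trunk mobility and fluctuations joined | Fat and fibre also joined |
|---|---|---|---|
| Pain | 2+1+2+2+1 = 8 | 7 | 7 |
| Impairment, quality of life | 2+2+4+2+4 = 14 | 12 | 10 |
| Force | 2+1+2+1 = 6 | 5 | 4 |
| Trunk | 2+2+4 = 8 | 4 | 3 |
| **Pairs** | **36** | **28** | **24** |
| Hypotheses joining more than two constructs | 13 | 9 | 7 |

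**False positives with all nulls true, each test at 0.05.** Applying 0.05 to every test is an assumption, since the plan gives that level only for sample size. The expected number is 0.05m under any dependence. The chance of at least one is 1 − 0.95^m if independent. For test statistics equicorrelated at 0.5 (assumed) it comes from numerical integration over a common normal factor.

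| m | Expected | At least one, independent | At least one, equicorrelated 0.5 |
|---|---|---|---|
| 17 | 0.85 | 58% | 39% |
| 24 | 1.2 | 71% | 46% |
| 36 | 1.8 | 84% | 55% |

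The tests share variables, so the independence column is illustrative. For 17 tests the true rate lies between 5% and the union bound of 17 × 0.05 = 85%. None of these counts includes the five separate sensory measures or the six measurement points in section 3.3, because 4.1 fixes no measurement point.

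**Status.** By the parameter lists in 2.2, the 17 hypotheses divide as follows:
- subjective against objective: 3 (pain) + 4 (impairment, quality of life) = 7;
- within subjective: 3;
- within objective: 4 (force) + 3 (trunk) = 7.

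Section 2.2 mentions only the first group, as secondary. Section 2.1 places all three under its primary-objective heading.

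**The case against.** The best reply is that this is an observational, single-centre inventory that already reads as exploratory. Section 2.2 speaks of possible relationships, 4.1 of correlations that are of interest, section 6.1 of limited generalizability. The protocol also reads like a translation, so the verb may be no more than ordinary H0/H1 language. This has weight: it makes the remedy a matter of wording, and it means a false claim could follow rather than will follow. It does not remove the point, because the sentence governing the list still promises proof or rejection and nothing labels the tests exploratory.

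A reader might infer more than the documents support:
- **That a multiplicity correction is required.** An openly exploratory correlation study does not need one, and it would be costly here. Bonferroni over 17 tests (0.05/17 = 0.0029) lowers power at r = 0.5 and n = 42 from 0.955 to 0.71 in the model that reproduces 42, and from 0.935 to 0.68 in the bivariate-normal model.
- **That 13 joint hypotheses, or 36 pairs, is a fact of the plan.** Section 2.2 treats trunk mobility and fluctuations under one parameter heading, and fat tissue and fibre alignment under another. The lower counts are equally fair readings.
- **That ten hypotheses have no status.** Section 2.2 says what the secondary objective includes, which need not be exhaustive. Their status is unclear rather than absent.
- **That the three sections carry three different lists.** Section 2.2 holds no hypotheses, and the eighteenth pair in 2.1 is a duplicate. The one substantive difference between 2.1 and 4.1 is quality of life in the fat and fibre hypothesis. Computing neurodynamics correlations without a hypothesis is a loose end, not a contradiction.

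**Conclusion.** The point holds as a mismatch between what the analysis can support and what 4.1 says it will conclude. With 17 hypotheses each tested once at 0.05 and all nulls true, 0.85 false positives are expected; the chance of at least one is 58% under independence and 39% with equicorrelation of 0.5. Unbundled into 24 to 36 pairs, 1.2 to 1.8 are expected, and the chance is 71% to 84% under independence. These figures rest on an assumed family size, on 0.05 being applied to each test, and on no relationship being real. They show how often chance could produce a relationship called proven, not how often it will. The conflict between 2.1 and 2.2 over status, and the missing decision rule for joint hypotheses, do not depend on them. This should be corrected, but it does not threaten the conduct of the study.

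**What to change.** 1. In 2.1 and 4.1, replace the proven-or-rejected wording with, for example: *All correlations are exploratory; none is regarded as confirmed because p < 0.05.* Report the coefficient with its 95% CI for every pair, and the total number of pairs tested.
2. Use one identical, unbundled list in 2.1 and 4.1, with the measurement point for each pair. Settle whether quality of life belongs in the fat and fibre hypothesis and whether neurodynamics is included. Define force by a patient-level rule, because the muscles tested follow each patient's affected nerve: for example, the affected side and the characteristic muscle of that nerve, with a stated rule for patients without radiculopathy.
3. Give the correlations one status. Extend the secondary objective in 2.2 to all three groups named in 4.1 (within subjective, within objective, between the two), and take the list out from under the primary-objective heading in 2.1.

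The cost is drafting in three sections, including some thought on the force rule. It needs no new data and no more patients, and no power is lost. The downside is that no single correlation can be claimed as confirmed. Chance findings will occur at the same rate; they will only no longer be called proven.

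If the sponsor wants a confirmatory claim, pre-specify one fully defined primary correlation at two-sided 0.05 and reconcile it with the primary objective in 2.2. At n = 42 under the bivariate-normal model its power is about 0.935 if the true correlation is 0.5, 0.76 at 0.4 and 0.50 at 0.3 (the lower values are assumed). Benjamini-Hochberg controls the false discovery rate across the list, does not support individual confirmatory claims, and should serve only as a screen.

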#### Pain Drawing (VAS)

---

H0 There is no correlation between pain and physical impairment and health-related quality of life.  
H1 There is a correlation between pain and physical impairment and health-related quality of life.

H0 There is no correlation between pain and activity diary.  
H1 There is a correlation between pain and activity diary.

H0 There is no correlation between pain and strength and muscle fiber alignment.  
H1 There is a correlation between pain and strength and muscle fiber alignment.

H0 There is no correlation between pain and trunk mobility and trunk fluctuations.  
H1 There is a correlation between pain and trunk mobility and trunk fluctuations.

H0 There is no correlation between pain and sensory activity.  
H1 There is a correlation between pain and sensory activity.

---

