## 4.2. Handling of missing data

Since statistical values of the individual relationships are determined, the data is also included if a test subject does not participate in all measurement points and/or measurements. Incomplete data from individual assessments (aborted tests) are not included in the final data analysis, but are recorded and stored.

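### Sections 2.1 and 4.1 let a null of no correlation be called proven; the planned tests cannot do that, and no interval, margin or rule for non-significant results prevents it

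*Combined protocol and SAP*

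**What the plan says.** Section 2.1 opens its list of hypotheses with "The following working and null hypotheses are to be statistically proven or discarded". Section 4.1 repeats the list after "The following working (H1) and null hypotheses (H0) are statistically proven or rejected". Both sentences name the working and the null hypotheses together and apply the same pair of outcomes to them.

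Each null is a point null, for example "There is no correlation between pain and activity diary". Section 4.1 lists 17 H0/H1 pairs (5 for pain, 5 for impairment and quality of life, 4 for force, 3 for trunk measures). Section 2.1 lists 18 (5 + 5 + 5 + 3).

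On the tests, section 4.1 says "The correlations are recorded using the 'Pearson Correlation tests' and 'Spearman Correlation tests". The sample size rests on a two-sided correlation test with "effect size = 0.5" and alpha and power of "0.05; power = 0.95"; the target is "42 based on these design specifications". Section 4.2 adds that "the data is also included if a test subject does not participate in all measurement points and/or measurements", while aborted tests are left out of the analysis.

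Sections 2.1, 4.1 and 4.2 contain no confidence interval, no equivalence margin and no statement of how a non-significant correlation is to be read.

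**The concern.** The two lead-in sentences are the only place where the plan says how test results become conclusions. On their face they allow two verdicts on a null: proven or rejected. A test of zero correlation can deliver only the second. When it does not reject, the data are compatible with zero and also with a range of non-zero correlations, and the plan asks for nothing that would show that range.

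This matters because section 1 presents the inventory of relations between pain and functional measures as a basis for supporting and improving physiotherapy, and section 8 foresees several articles. A conclusion that two measures are unrelated, drawn only from a p-value above 0.05, would be unsound, and the current text does not rule it out. The point is separate from multiplicity: it concerns false statements of absence, not the number of tests.

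**Working it through.** **Inputs from section 4.1.** Two-sided test, alpha 0.05, power 0.95, effect size r = 0.5, n = 42.

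**Assumptions, because the plan does not settle them.** One value per patient per variable (the plan has six measurement points and does not say which feeds a correlation), all 42 patients contributing, bivariate normal data, Pearson test.

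**1. The plan's own figure.** In the point-biserial model, t has n - 2 degrees of freedom and noncentrality sqrt(n) * r / sqrt(1 - r^2). At n = 42 this is 6.481 * 0.5 / 0.866 = 3.742, and power is 0.9545. At n = 41 power is 0.94995, just short of 0.95. So n = 42 is reproduced exactly. The exact bivariate-normal model gives n = 46, with power 0.935 at n = 42; the difference is small and is not the issue here.

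**2. Critical value at n = 42.** t(40; 0.975) = 2.021, so |r| = 2.021 / sqrt(40 + 2.021^2) = 0.304. Any smaller observed |r| is non-significant.

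**3. Probability of a non-significant result.** This is the exact density of r at n = 42, integrated between -0.304 and 0.304:

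| True correlation | Power | Non-significant |
|---|---|---|
| 0.2 | 0.247 | 75% |
| 0.3 | 0.497 | 50% |
| 0.4 | 0.764 | 24% |
| 0.5 | 0.935 | 6.5% |

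**4. What a non-significant result leaves open.** Fisher z interval: tanh(atanh(r) ± 1.96 / sqrt(39)), with 1.96 / sqrt(39) = 0.314.

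- Observed r = 0: tanh(±0.314) gives -0.30 to 0.30.
- Observed r = 0.29, non-significant: atanh(0.29) = 0.299, so tanh(-0.015) to tanh(0.612) gives -0.02 to 0.55. This interval contains the plan's own design value of 0.5.

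**5. Sensitivity to Spearman.** An approximate version with Fisher z and variance 1.06 / (n - 3) gives power 0.233, 0.467, 0.729 and 0.915 at 0.2, 0.3, 0.4 and 0.5, so about 77%, 53%, 27% and 8.5% are non-significant. Fewer than 42 contributing patients, which section 4.2 allows, would raise these rates further.

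**6. Sample size or margin?** A claim of absence needs a margin m. With two one-sided 5% tests on the Fisher z scale and a true correlation of 0, power is 2 * Phi(atanh(m) * sqrt(39) - 1.645) - 1, or 0 if that is negative. The margins below are assumed, since the documents give none:

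| Margin | Power at n = 42 | n for 80% power |
|---|---|---|
| 0.2 | 0% | 212 |
| 0.3 | 23% | 93 |
| 0.4 | 68% | 51 |
| 0.5 | 93% | 32 |

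Whether 42 patients could support absence depends entirely on the margin. With no margin, no sample size can.

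**The case against.** The strongest reply is that this is loose wording. Both sentences are lead-ins to a list and can be read distributively: the working hypothesis is proven, the null is rejected. The English also reads like a translation (trunk sway appears in places as hull swaying), so one verb should not carry much weight. This reading is available, and it lowers the severity. It does not remove the gap, because it still leaves the plan silent on what follows from a non-significant test.

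A reader might go further and infer that every non-significant pair will be published as a proven lack of relation, or that useful assessments will be dropped. The documents do not support either. No section says how null results will be reported or that any assessment will be abandoned. Section 2.2 makes relationships the secondary objective, and section 6.2 speaks of connections becoming recognizable, which is about finding relations rather than excluding them.

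A reader might also conclude that the fault lies in having only 42 patients, or that moderate correlations are bound to be missed. Neither follows. The main fault is the absent margin, and a true 0.4 would be detected about 76% of the time and a true 0.5 about 93%.

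Finally, it is tempting to take 0.5 as a ready-made margin. Section 4.1 gives it only as a size to detect, never as a bound below which a correlation is unimportant.

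**Conclusion.** The point holds as a matter of wording and interpretation. Taken literally, sections 2.1 and 4.1 permit a conclusion that the planned tests cannot give, and nothing else in the plan blocks it. The miss rates in the working show why it would be unsafe to read non-significance as absence: about three in four at a true correlation of 0.2, half at 0.3, a quarter at 0.4, and few at the design value.

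Those rates rest on one value per patient, 42 complete pairs, bivariate normality and Pearson. They illustrate the problem and are not the study's actual error rates. The logical point depends on none of them.

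Severity is minor to moderate: no test, estimate, sample size or data collection changes, but what the study may conclude does.

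**What to change.** - In sections 2.1 and 4.1, replace the lead-in wording with: H0 is rejected or not rejected.
- In section 4.1, add that every correlation is reported with its 95% confidence interval and the number of patients contributing.
- In section 4.1, add that a non-significant result is not in itself evidence of no correlation and is interpreted from its interval.
- Use a formal statement of absence only if the sponsor itself sets in advance, with reasons, a margin of unimportant correlation. Otherwise leave such statements out.

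Cost: a few sentences in the plan and extra table columns for the interval and the number contributing. Some non-significant results will have to be called inconclusive. No new data are needed.
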